The emergent bumetanide safety profile observed in paediatric population with ASD was mainly related to bumetanide diuretic effect (enuresis, pollakiuria, polyuria, electrolyte disturbances and dehydration) and was dose-related. It did not differ from that of bumetanide tablets. Hypokalaemia is an identified risk and therefore blood potassium level will be regularly monitored during the phase III bumetanide paediatric program (blood potassium sampling schedule validated with the EMA). It has to be highlighted that all hypokalaemia reported during the phase II NeuroClin02 dose-range study were asymptomatic (and without any cardiac impact), and thus it is crucial to perform all planned samplings. Lastly, the most favourable tolerability profile was observed with bumetanide 0.5 mg twice a day corresponding to the dose that will be given during the 2 phase III studies.

Considering the targeted population of patients, a Data Monitoring Committee (DMC) will be set up and will be responsible for periodic review of patient's safety data throughout the study. Details on the role and organisation of the DMC will be provided in a separate charter. The study will be carried out in compliance with the protocol, GCP, the ethical principles that have their origin in the Declaration of Helsinki and the applicable regulatory requirements.

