Blood electrolytes monitoring (K, Na) (performed locally except at ASSE)	X		X	X	X	X	X ⁽³⁾	X	X ⁽³⁾	X ⁽³⁾	X			
ECG	X ⁽⁶⁾					X ⁽³⁾	X ⁽³⁾	X ⁽³⁾					X ⁽³⁾	
Renal ultrasound	X												X ⁽³⁾	
Sitting and standing blood pressure/Heart rate	X	X			X			X					X	
Body Weight and Height	X	X ⁽⁴⁾			X ⁽⁴⁾	X ⁽⁴⁾	X ⁽⁴⁾	X	X ⁽⁴⁾	X ⁽⁴⁾	X		X	
Pharmacokinetics (blood samples)								X					X	
Other measurements														
PedsQL		X				X		X					X	
WHOQOL-Bref		X				X	X	X					X	
EQ5D-3L		X						X					X	
Acceptability Questionnaire													X	

(1) CGI-S only

(2) CGI-4 only

(3) Prescribed based on the clinical opinion of nephrologist or investigator

(4) Only body weight

(5) Results of the exam should be available at this visit prescription to be done at the previous visit

(6) ECG Triplicate only at ASSE

Table (4.2.2) 1 – Investigation schedule (continued)

	Open label 26 week active treatment period									FU	WD Withdrawal visit to be undergone in case of IMP definitive discontinuation or in case of total withdrawal from the study whatever the period
	W026 48/72h	W026 Day 10	W026 Day 17 (D199)	W030	W034	W038	W042	W046	W052		
Concomitant treatments ⁽¹⁾	X	X	X	X	X	X	X	X	X	X	X
IRS				X	X	X	X	X			
IMP allocation				X	X	X	X	X			
IMP definitive discontinuation											X
IMP dispensation				X	X	X	X	X			
Oral solution volume adaptation to patient weight				X	X	X	X	X			
Compliance IMP				X	X	X	X	X	X		X
Efficacy measurements											
CARS2-HF/ CARS2-ST ³ /CARS2-QPC						X			X	X	X ^{(6) (7)}
CGI						X ⁽⁶⁾			X	X	X ⁽⁶⁾
SRS-2						X			X	X	X ^{(6) (7)}
VABS II									X		X ^{(6) (7)}
Safety measurements											
Suicidality (C-SSRS-C)						X			X		X
Adverse events	X	X	X	X	X	X	X	X	X	X	X
PAERS scale			X	X	X	X	X	X	X		X
Laboratory tests (blood and urine)						X			X		X
Blood electrolytes monitoring (K, Na) (performed locally except at WD)	X	X	X	X	X ⁽⁴⁾	X	X ⁽⁴⁾	X ⁽⁴⁾	X		X
ECG				X ⁽⁵⁾	X ⁽⁵⁾	X ⁽⁵⁾			X ⁽⁵⁾		X
Renal ultrasound									X ⁽⁵⁾		X
Sitting and standing blood pressure/ Heart rate			X			X			X		X
Body Weight and Height			X ⁽⁶⁾	X ⁽⁶⁾	X ⁽⁶⁾	X	X ⁽⁶⁾	X ⁽⁶⁾	X		X
Other measurements											
PedsQL				X		X			X		X ^{(6) (7)}
WHOQOL-Bref				X	X	X			X		X ^{(6) (7)}
EQ5D-3L						X			X		X ^{(6) (7)}
Acceptability Questionnaire									X		X ⁽⁷⁾

(1) Including non-pharmacological therapies (psychotherapy, social skills training, behavioural interventions, etc)

(2) Prescribed based on the clinical opinion of nephrologist or investigator

(3) Only body weight

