relevant hypercalciuria according to their clinical judgment (based on broader sources including risk factors, medical history, clinical examination and other biological parameters).

Additional urinary retest(s) and other appropriate exams should be performed if they judge them as relevant for the patient's safety.

- Absence of 2 consecutive planned electrolytes monitoring analysis.
- Absence of 2 consecutive planned urinary monitoring analysis.
- Occurrence of QT prolongation ($QTc_F \geq 480\text{ms}$), torsade de pointe and ventricular arrhythmia. Even if a 12-lead ECG reading and interpretation will be centralised, a local assessment of ECG exams is necessary for detection of medical urgencies and must be enclosed in the source data. Central reading reports for ECG overrule local reading for inclusion/exclusion/withdrawal criteria.
- Occurrence of a new psychiatric or other medical conditions leading to necessary administration of forbidden concomitant medication or likely to interfere with the conduct of the study.
- Any event or circumstances related or unrelated to the treatment justifying the discontinuation of treatment in the investigator's opinion (including treatment failure i.e. lack of efficacy).
- Major deviation to protocol if it interferes with the study evaluations and/or if it jeopardises participant's safety, e.g. any medical event requiring administration of an unauthorised concomitant treatment (see section 6.3).

Other criteria for premature discontinuation of IMP and for premature withdrawal from the study:

- Lost-to-follow up.
- Any non-medical circumstances leading to patient withdrawal (e.g. assent/consent withdrawal).

Information to be collected during the last visit of these participants is given in Section 5.6.2. These follow-up modalities are used to ensure the efficacy and safety evaluation of all participants who received the IMP.

Special conduct in case of gastrointestinal symptoms and weight loss

If the patient experiences digestive symptoms (≥ 3 liquid stools per day and/or ≥ 3 vomits per day) or digestive symptoms with a weight loss greater than 5%, the study treatment should be temporarily interrupted. Such an interruption will last 48h/72hours.

In such a case a monitoring of K^+ , Na^+ must be done locally prior to study treatment re-introduction. Further electrolytes follow up will be locally done according to the clinical opinion of the medical doctor.

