- During the Double blind treatment period it will be prescribed at W020 and the assessment of the recording must be available for/during at W026 visit
- During the Open label treatment period it will be prescribed at W046 and the assessment of the recording must be available for/during at W052 visit
- At the withdrawal visit in case of premature withdrawal.

This exam could be done within 7 days prior to the day of the visit.

This exam should be assessed by a nephrologist or by a qualified specialist who will transmit the renal assessment to the investigator. As far as possible the same nephrologist/qualified specialist will assess renal ultrasound exams for a given patient all along the study.

Biological Safety measurements

To ensure homogeneity of the results, all biological assessments (except Na⁺/K⁺ parameters under treatment) will be carried out by the central laboratory chosen by I.R.I.S. The reference values of measured parameters will be mentioned in each laboratory report.

Biological results will be sent to site from central laboratory via a laboratory report, with the exception for Na⁺/K⁺ parameters which will be assessed locally (except at the selection visit before the first IMP intake and at the withdrawal visit (WD) after the last IMP intake. All laboratory reports (central and local) should be assessed by investigator and kept in the patient's medical file.

The sampling process and storage conditions on site will be described in the laboratory manual provided by the central laboratory.

The laboratory tests will be performed:

- Selection visit (laboratory tests will be prescribed at), so that the results are available for the inclusion visit
- During the double blind treatment period at W000+48/72h (only Na⁺/K⁺), W000+Day10 (only Na⁺/K⁺), W000+Day17 (only Na⁺/K⁺), W004 (only Na⁺/K⁺), W012 and W026 visits
- During the open-label extension period, at W026+48/72h (only Na⁺/K⁺), W026+Day10 (only Na⁺/K⁺), W026+Day17 (only Na⁺/K⁺), W030 (only Na⁺/K⁺), W038 and W052 visits
- At the withdrawal visit in case of premature withdrawal

The results should be checked carefully by investigator once received, and the patient/parent/legal representative(s) or caregiver (when applicable) should be contacted again to inform them about results and any abnormality that necessitates a specific follow-up.

Laboratory tests at Selection visit

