At selection visit, blood and urinary test samplings will be prescribed. All the results of these examinations must be available for the inclusion visit.

The following parameters will be analysed on blood samplings:

- **Biochemistry parameters:** sodium, potassium, calcium, chloride, magnesium, bicarbonates, phosphor, urea, uric acid, creatinine, creatinine clearance-eGFR (Schwartz formule 2009), AST, ALT, total bilirubin, free bilirubin, conjugated bilirubin, (ALP), Gamma-Glutamyltransferase (gamma GT), total cholesterol, HDL and LDL cholesterol, triglycerides, glucose, protein (Total, Albumin)
- **Haematology parameters:** haemoglobin, haematocrit, erythrocytes, white blood cells count, platelets, MCV.
- **Screening for hepatitis A, B and C** serologic markers.

The following parameters will be analysed on urinary samplings:

- **Calciuria, proteinuria and creatininuria**

Laboratory tests during the study:

The following parameters will be analysed on blood samplings:

- **Biochemistry parameters:** sodium, potassium, calcium, chloride, magnesium, bicarbonates, phosphor, urea, uric acid, creatinine, creatinine clearance (Schwartz formule 2009), AST, ALT, total bilirubin, free bilirubin, conjugated bilirubin, (ALP), Gamma-Glutamyltransferase (gamma GT), total cholesterol, HDL and LDL cholesterol, triglycerides, glucose, protein (Total, Albumin).
- **Haematology parameters:** haemoglobin, haematocrit, erythrocytes, white blood cells count, platelets, MCV.

The following parameters will be analysed on urinary samplings:

- **Calciuria, proteinuria and creatininuria**

		BLOOD ANALYSIS			URINE ANALYSIS
		Biochemistry excluding Na/K	Na/K monitoring via local laboratory	Haematology	Calciuria, Creatininuria Proteinuria
Double blind treatment period	W000 + 48/72h		X		
	W000 + Day 10		X		
	W000 + Day 17		X		
	W004		X		
	W012	X	X	X	X
	W026	X	X	X	X
Open label treatment period	W026 + 48/72h		X		
	W026 + Day 10		X		
	W026 + Day 17		X		
	W030		X		
	W038	X	X	X	X
	W052	X	X	X	X

Additional laboratory tests could be performed during the study if the medical doctor deems them as necessary.

ELECTROLYTES MONITORING

In the framework of this study the monitoring of electrolytes under treatment will be assessed locally. This will allow saving time in the delivery of laboratory results and to manage the Potassium supplementation when needed.

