Investigators should always encourage patients to eat foods containing potassium as soon as they know that they will be included in the study. See [Table \(8.2\) 1](#)

Table (8.2) 1 - Foods that have a higher potassium contents

Fruit and nuts	Fruit in particular - bananas, apricots, avocados, blackcurrants, rhubarb, fresh fruit juices Dried fruits eg currants, raisins, prunes, figs, sultanas, are rich sources of potassium All varieties of nut eg almonds, peanuts and walnuts
Potatoes	Potatoes are very rich sources of potassium if they are not boiled Jacket potatoes Ordinary fried chips Instant potato products eg waffles, potato croquettes Potato crisps
Vegetables and pulses	In particular - sprouts, mushrooms, parsnips, spinach, baked beans, kidney beans, lentils
Cereals	Cereals which are high in bran eg bran flakes, all bran, muesli
Biscuits, cakes and sweets	Fruit cakes, fig rolls, muesli bars Chocolate, fudge, liquorice
Milk and dairy products	Drinking milk or eating yoghurts

The first electrolytes monitoring under treatment, in both double and open label periods, should be performed locally no later than 72h after W000 and W026 respectively.

In case of any abnormality, electrolytes will be monitored until return to normal values.

In case of **Mild Hypokalaemia ($3\text{mEq/L} \leq \text{K}^+ < 3.5 \text{mEq/L}$)** arising under study treatment:

→ Foods containing Potassium will be recommended such as leafy green vegetables, tomatoes, citrus fruits, oranges or bananas. An adequate care should be implemented for the hypokalaemia follow up.

→ Patient will be supplied with oral potassium according to investigator's opinion which can be based on local guidelines or local medical practice. The dose could be adapted to hypokalaemia severity or patients' weight.

The following Potassium Chloride doses are recorded only for indicative purposes:

- <20 kg = 400 mg/day (200 bid)
- 20-40 kg = 600 mg/day (300 bid)
- 40 kg = 1200 mg/day (600 bid)

In case of **Moderate Hypokalaemia ($2.2\text{mEq/L} \leq \text{K}^+ < 3 \text{mEq/L}$)** arising under study treatment:

→ The study treatment should be immediately discontinued.

→ An adequate care should be implemented for the hypokalemia follow up.

→ Cardiac monitoring will be performed and level of potassium should be monitored until return within normal range

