3.6.3. Clinical laboratory evaluation

Definition:

- A laboratory value is considered as analysable if non-missing and not flagged in the ClinTrial database as "not analysable".
- The analyses will be performed on periods #2, #4 and #6.
- A value is considered as occurring during the considered period if the sampling date is between the start and last date of the considered period.
- Baseline for each period is defined in Section 3.1.2.
- For each considered period:
 - High emergent abnormal value under treatment according to the laboratory reference ranges is defined as value \leq ULN (Upper Limit of Normal laboratory reference range) or missing at the baseline of the considered period and $>$ ULN under treatment.
 - Low emergent abnormal value under treatment according to the laboratory reference ranges is defined as value \geq LLN (Lower Limit of Normal laboratory reference range) or missing at baseline of the considered period and $<$ LLN under treatment.

- High emergent abnormal value under treatment according to the cut-offs for PCSA values is defined as value \leq ULS (Upper Limit used to define potentially clinically Significant abnormal values) or missing at baseline of the considered period and $>$ ULS under treatment.
- Low emergent abnormal value under treatment according to the cut-offs for PCSA values is defined as value \geq LLS (Lower Limit used to define potentially clinically Significant abnormal values) or missing at baseline of the considered period and $<$ LLS under treatment.

Analyses:

For each biochemical, haematological (blood and urine sample) parameter and for electrolytes monitoring (Potassium, Sodium), the following analysis will be performed for each period:

- Number and percentage of patients with at least one high/low emergent abnormal value under treatment, according to the laboratory reference ranges and to the cut-offs for PCSA values.
- Laboratory parameters classified (number and percentage of patients in each class) according to these reference ranges and cut-offs and using shift tables from baseline in the considered period to the worst (high and/or low) values under treatment.

Moreover, listings of patients with out-of-range or PCSA analysable values emergent under treatment in each period and of non-analysable values excluded from analyses will be provided.

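### Opinion-driven sodium and potassium draws enter the by-arm laboratory tables, so part of a between-arm difference in the double-blind period can reflect how often children were tested

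*Protocol*

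**What the plan says.** **Sampling.** Protocol 8.2 and Table (4.2.2) 1 schedule six on-treatment Na/K draws for every child in the double-blind period: W000+48/72h, Day 10, Day 17, W004, W012 and W026. At W008, W016 and W020 the electrolyte row carries the footnote "Prescribed based on the clinical opinion of nephrologist or investigator". Further samples can arise in three ways:

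- at the doctor's discretion (Protocol 8.2): "Additional laboratory tests could be performed during the study if the medical doctor deems them as necessary";
- after gastrointestinal symptoms (Protocol 5.6.1): "Further electrolytes follow up will be locally done according to the clinical opinion of the medical doctor";
- after an abnormal result (Protocol 8.2): "In case of any abnormality, electrolytes will be monitored until return to normal values".

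**Analysis.** SAP 3.6.3 decides which results count by date: "A value is considered as occurring during the considered period if the sampling date is between the start and last date of the considered period". It then reports "Number and percentage of patients with at least one high/low emergent abnormal value under treatment", shift tables to the worst value, and hypokalaemia by severity. SAP 3.6 presents these by arm for the double-blind period. The open-label and combined periods each show a single arm. SAP 3.6.4.1 and 3.6.4.2 describe vital signs and ECG parameters at planned visits. SAP 3.6.3 has no such restriction and does not ask for the number of samples per child.

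**The concern.** Protocol section 2 describes the safety profile in children with ASD as "mainly related to bumetanide diuretic effect (enuresis, pollakiuria, polyuria, electrolyte disturbances and dehydration) and was dose-related". A clinician can see several of these effects without knowing the allocation, and they are natural reasons to order an optional electrolyte check. The opinion-based draws can therefore be more frequent on bumetanide even if the drug had no effect on sodium or potassium.

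A percentage with any abnormal value rises with the number of looks, and the worst of several values can only get worse as values are added. If one arm is sampled more, both summaries move against it. Section 2 also reports that all phase II hypokalaemia was without symptoms, so detection depends on sampling. Potassium below 3.5 mEq/L is the protocol's adverse event of special interest (8.6). A reader of the by-arm percentages would have no means of separating drug effect from testing intensity.

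**Working it through.** **1. What the plan quantifies.** The documents give no expected number of extra draws and no abnormality rate per draw. The one related figure is the 34 mL blood maximum in Table (4.2.2) 3. It reproduces from scheduled visits alone: 6+1+1+1+1+5.5+5.5 = 21 mL to W026, then 1+1+1+1+4.5+4.5 = 13 mL, total 34 mL. Six of the draws to W026 are on-treatment Na/K draws.

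**2. Optional draws, no drug effect.** Let p be the chance of an abnormal value per draw, equal in both arms and independent between draws, and f the share of the three optional draws taken. Both are assumptions.

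P(any abnormal) = 1 − (1−p)^6 × (1−pf)^3

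If instead a fixed share s of bumetanide children have all three optional draws and placebo children have none, the false difference is s × [(1−p)^6 − (1−p)^9]. At p = 2% and s = 40%: 0.4 × (0.8858 − 0.8337) = 2.1 points.

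| p | 6 draws | 9 draws | all three v none | 40% of children v none | 50% v 20% uptake | 30% v 10% uptake |
|---|---|---|---|---|---|---|
| 1% | 5.9% | 8.6% | 2.8 | 1.1 | 0.8 | 0.6 |
| 2% | 11.4% | 16.6% | 5.2 | 2.1 | 1.6 | 1.1 |
| 2.5% | 14.1% | 20.4% | 6.3 | 2.5 | 1.9 | 1.3 |
| 3% | 16.7% | 24.0% | 7.3 | 2.9 | 2.2 | 1.5 |
| 5% | 26.5% | 37.0% | 10.5 | 4.2 | 3.2 | 2.2 |

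The last four columns are false differences in percentage points, from unrounded values. The fourth column is the most these three visits can produce. Tests added at discretion have no stated limit and are not included.

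**3. Retests after an abnormal value.** A child retested for low potassium already counts as having a low potassium. Simulating 400,000 children at p = 2.5% gives 14.12% with and without such retests. A retest can act only through the other electrolyte on the same draw, the opposite direction, the category of potentially clinically significant abnormal (PCSA) values or severity class, and the worst value. With equal risk in both arms and retests triggered by either electrolyte, low potassium moves from 14.2% to 14.4% and low sodium from 14.1% to 14.5%. Moderate-or-worse potassium (assumed 0.3% per draw) moves from 1.81% to 1.86%. These shifts are small and occur in both arms alike.

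For such retests to differ by arm there must be a real effect on some electrolyte. Suppose low potassium has a 10% chance per draw on bumetanide and 2% on placebo, with half of abnormal values persisting at each retest. Low sodium then shows about 16.5% against 14.7% with no effect on sodium. That spill-over rests on a true potassium effect.

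**4. Scheduled draws only.** With the six scheduled draws and no drug effect, both arms have the same expected percentage: 5.9% at 1%, 14.1% at 2.5%, 26.5% at 5%. The testing-induced difference is 0, apart from early stopping and missed draws.

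**The case against.** **The size is uncertain and probably modest.** Footnoted visits and discretionary tests apply to both blinded arms, so no extra draws on placebo is an extreme assumption. At 1% per draw, moderate imbalance gives under 1 point. With about 100 children per arm and 12% incidence, the standard error of a difference is √(2 × 0.12 × 0.88 / 100) = 4.6 points, larger than most of these biases. This stands, and it limits the point to interpretation of descriptive tables.

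**Other rules work the opposite way.** Treatment stops at potassium below 3 mEq/L (Protocol 5.6.1 and 8.2). Laboratory analysis uses period #2, which ends at the earlier of last double-blind intake plus 2 days and first open-label intake (SAP 3.6). Much follow-up of moderate or severe hypokalaemia is therefore not counted, and children who stop early miss later scheduled draws. This stands too, so the net direction is not established. It does not remove retests for mild hypokalaemia, for which 8.2 requires no stop, nor the optional visits of children who continue.

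**Nothing is tested.** SAP 3.4.1 gives a p-value only for the primary analysis, and SAP 3.6.3 lists individual patients with emergent abnormal values. True, but the by-arm percentages will still be read as a comparison.

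**Some of this cannot be checked.** Table templates are in a separate document, and the documents do not say that every unscheduled local result reaches the database. If few do, the concern shrinks.

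**Conclusion.** The point holds for the opinion-based draws. SAP 3.6.3 lets samples whose frequency may depend on visible drug effects into any-abnormal, worst-value and severity summaries shown by arm, with neither a planned-visit version nor a count of samples. Under the assumptions above the false difference is about 1 to 3 points for moderate imbalance at 2% to 5% per draw, under 1 point at 1%, and at most 6.3 points from the three visits at 2.5%. Per-draw risk, uptake by arm and independence between draws are assumptions. Early stopping may offset part or all of it.

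Two stronger readings are tempting and not supported. A reader might infer that retesting until normal inflates the bumetanide percentage by itself. It does not: the child is already counted for that analyte, direction and cut-off, and retests differ by arm only if some electrolyte is truly affected. A reader might also assume many extra draws on one arm. Six extra independent draws in 40% of bumetanide children and none on placebo would give 0.4 × (0.98^6 − 0.98^12) = 4.0 points at 2%. The schedule contains only three optional visits in this period, and retests are not fresh chances of a first abnormal value for the same analyte.

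**What to change.** In SAP 3.6.3, for the double-blind period:

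1. Keep the all-samples tables as they are.
2. Beside them, add the Na/K any-abnormal, worst-value shift and hypokalaemia-severity tables restricted to the scheduled visits (W000+48/72h, Day 10, Day 17, W004, W012, W026).
3. Report the number of Na/K samples per child by arm.

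The cost is one repeated set of tables and one descriptive row. No new procedure is needed and no change to clinical monitoring is proposed. The sponsor should confirm that unscheduled local results are in the database, because the sample count depends on it.

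The restricted tables leave out real events found on extra or withdrawal-visit draws and do not correct for early stopping. They are companions to the all-samples tables, to be read together with them, and should not replace them.
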